4.1.2 Biomarker Population

A Biomarker population is defined as all enrolled patients who (a) received at least one infusion of Ocrelizumab, even if the infusion was incomplete and (b) received two LPs. Summaries of biomarkers in this population were performed in *Interim Analysis 1*.

4.1.3 Pharmacokinetic-Evaluable Population

The definition of pharmacokinetic evaluable population will be specified in a separate analysis plan together with the pharmacokinetic endpoints, if applicable.

4.1.4 Safety Population

Safety population is defined as all enrolled patients who received at least one infusion of ocrelizumab, even if the infusion was incomplete. Summary of safety outcome measures will be performed using the safety population. Patients will be summarized by the actual “arm” depending on when the patient actually received the 2nd LP.

4.2 ANALYSIS OF STUDY CONDUCT

The following information on patient disposition will be summarized using the ITT population by the actual arm:

- Number and percentage of patients who received ocrelizumab treatment during the Main Treatment Period and the Long-term Extension Period.
- Number and percentage of patients who received LP at each scheduled visit.

- Number and percentage of patients who completed the Main Treatment Period and the Long-term Extension Period of the study.
- Reason for study discontinuation. At interim analysis, patients who haven't filled out the Study Completion CRF by the CCOD of analyses will be considered as "ongoing" in study.
- Reason for discontinuation from ocrelizumab during Main Treatment Period and the Long-term Extension Period. At interim analysis, patients who haven't filled out the Ocrelizumab Completion/Discontinuation CRF by the time CCOD will be considered as "ongoing" on treatment.
- Summaries or listing of major protocol violations.

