4.4 EFFICACY ANALYSIS

All biomarker assessments (scheduled or unscheduled) will be summarized after applying visit windows. Summary of the visit windowing rules can be found in Appendix 2. See Module 3 for full visit window specifications. If multiple values of the same parameter occur within the same time window for blood biomarkers

Ocrelizumab—Genentech, Inc.

15/Statistical Analysis Plan ML29966

or regular lab values, the worst value for that parameter will be presented in the summary table. If multiple MRI scans occur within the same time window, the scan closest to the scheduled visit date will be included in the analysis.

All summaries will be done based on the ITT population and summaries will be provided by the actual arm, as determined by the actual timing of 2nd LP:

For patients randomized to Arm 1-3,

If the second LP date is missing then patient is included in the arm where originally randomized to;

Else:

Study Day of second LP (= date of the 2nd LP – 1st infusion start date +1)	Treatment Arm
≤126	Arm 1
127-266	Arm 2
≥267	Arm 3

Patients randomized to Arm 4 will be summarized as Arm 4 regardless of the timing of 2nd LP.

Unless otherwise specified and where appropriate, statistical tests, if any, will be performed at the two-sided 5% significance level. Corresponding 95% confidence intervals will be presented as appropriate. No corrections for multiple testing will be applied.

For biomarkers measured below the lower limit of quantification (LLOQ), numeric values will be imputed using half of the LLOQ.

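### For RMS Arms 1–3, the lumbar puncture table groups patients by when the second LP was done, so it cannot show adherence to the randomised LP time

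*SAP*

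**What the plan says.** SAP 4.2 sets the population and grouping for all disposition items: "The following information on patient disposition will be summarized using the ITT population by the actual arm". One of these items is "Number and percentage of patients who received LP at each scheduled visit".

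SAP 4.4 explains the grouping: "summaries will be provided by the actual arm, as determined by the actual timing of 2nd LP". The rule opens with "For patients randomized to Arm 1-3". A second LP on or before study day 126 places the patient in Arm 1, days 127–266 in Arm 2, and day 267 or later in Arm 3. Two provisions limit it:

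- For an LP that was not done: "If the second LP date is missing then patient is included in the arm where originally randomized to".
- For the delayed-start control arm: "Patients randomized to Arm 4 will be summarized as Arm 4 regardless of the timing of 2nd LP".

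No reassignment rule is given for the PPMS cohort. SAP 4.1.1 gives the only reason for using actual arm, which is a more accurate account of biomarker effects over time. SAP 4.1.4 applies the same grouping to safety. The supplied text specifies neither an LP table by randomised arm nor a cross-table of randomised by actual arm.

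**The concern.** Arms 1–3 receive the same treatment and differ only in when the second LP is due. Having the LP at the assigned time is therefore the main thing that a per-arm conduct table can show. Here the row groups patients by the outcome it reports. A patient randomised to Week 12 and punctured on day 200 leaves Arm 1 and appears as a completed Week 24 LP in Arm 2.

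The reader would not learn how many patients missed their randomised LP time, or whether those patients differ from the rest. The stated reason for actual arm concerns biomarker time course and does not extend to disposition.

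**Working it through.** The documents give no LP-completion figure to reproduce. The check has two parts: whether the grouping rule and the visit windows coincide, and what that does to the percentages.

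**Inputs**

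- Cut points for actual arm: SAP 4.4.
- CSF visit windows: SAP Appendix 2.
- Planned arm sizes 16, 28 and 28 (72 randomised) and an allowance of about 10% for missing post-treatment CSF: SAP 2.3.
- Second LP due on day 84, 168 or 364, each ±7 days: Protocol Appendix 1.
- Numbers of patients who move or have no second LP: not in the documents, so assumed below.

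**Step 1: rule against window**

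| Study day of second LP | Actual arm (SAP 4.4) | CSF window (SAP Appendix 2) |
|---|---|---|
| 2–126 | Arm 1 | Week 12 |
| 127–266 | Arm 2 | Week 24 |
| 267 to the day before LTE Day 1 | Arm 3 | Week 52 |
| LTE Day 1 or later | Arm 3 | Week 144 or later |

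With LTE Day 1 at its nominal day 504, the two agree on every day from 2 to 503. Any second LP in that range fills the visit window of the arm it defines.

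**Step 2: formula**

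For one arm, let N be the number randomised, m those with no second LP, o those moved out and i those moved in.

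- By randomised arm: R = (N − m − o)/N
- By actual arm: A = (N − m − o + i)/(N − o + i)

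Cross-multiplying, A ≥ R is equivalent to o(N − m − o) + i(m + o) ≥ 0. This always holds because N − m − o cannot be negative. If o = i = 0, then A = R.

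**Step 3: Arm 2 alone, assumed counts (N = 28, o = 4, i = 0)**

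- m = 0: R = 24/28 = 85.7%; A = 24/24 = 100%; gap 14.3 points.
- m = 3 (3/28 = 10.7%, close to the plan's allowance): R = 21/28 = 75.0%; A = 21/24 = 87.5%; gap 12.5 points.

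**Step 4: three arms together, assumed 1/3/3 missing**

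| Assumed moves | Grouping | Arm 1 | Arm 2 | Arm 3 | All |
|---|---|---|---|---|---|
| None | Either | 15/16 (93.8%) | 25/28 (89.3%) | 25/28 (89.3%) | 65/72 (90.3%) |
| 1 from Arm 1 to 2, 2 from Arm 2 to 3 | Randomised | 14/16 (87.5%) | 23/28 (82.1%) | 25/28 (89.3%) | 62/72 (86.1%) |
| Same | Actual | 14/15 (93.3%) | 24/27 (88.9%) | 27/30 (90.0%) | 65/72 (90.3%) |
| 3 from Arm 1 to 2, 4 from Arm 2 to 3 | Randomised | 12/16 (75.0%) | 21/28 (75.0%) | 25/28 (89.3%) | 58/72 (80.6%) |
| Same | Actual | 12/13 (92.3%) | 24/27 (88.9%) | 29/32 (90.6%) | 65/72 (90.3%) |

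The share with any second LP is 65/72 throughout. Only completion at the assigned time changes with the grouping. Arm 3 rises slightly although nobody leaves it, because the patients who move in all have an LP.

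**Step 5: how far an LP must slip**

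Leaving Arm 1 by lateness needs day 127, which is 127 − 84 = 43 days late. Leaving Arm 2 needs day 267, which is 267 − 168 = 99 days late. A smaller slip does not change the arm but is hidden by the width of the window. For example, day 120 is 36 days late and still counts as Week 12.

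**The case against.** A reader might infer that the table hides every failure and overstates completion by construction. The documents do not support that.

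- **Missed LPs.** A patient with no second LP date stays in the randomised arm's denominator, so an LP never done shows as not done. Arm 4 is exempt and PPMS has no reassignment rule.
- **Size.** The overstatement depends on patients moving, and delays of 43 or 99 days may be rare. It equals the share that moved out only when no LP is missing (12.5 points, not 14.3, in the second Arm 2 case).
- **Other places it could show.** SAP 4.2 also summarises or lists major protocol violations, which might include mistimed LPs, though it does not say so. A second LP on or after LTE Day 1 would leave Week 52 empty. SAP 4.2 does not say whether visits are windowed or nominal. Under nominal labels, a late Week 12 LP would appear under Week 12 in another arm. The output list (Module 2) and full window rules (Module 3) were not available.
- **Safety.** A reader might also infer that the safety tables are distorted, since "Patients will be summarized by the actual “arm” depending on when the patient actually received the 2nd LP". Arms 1–3 have the same treatment and no between-arm safety comparison is planned, so regrouping changes no total and no planned comparison.

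These limits stand and narrow the point. They do not make adherence to the randomised time readable from the specified table. One limit is also weaker than it looks, because the SAP does not define the second LP where optional samples exist. The synopsis in SAP Appendix 1 offers an optional Week 52 LP in Arms 1, 2 and 4 and an optional LP at relapse. If the second LP means the second in time, an Arm 1 patient who skips Week 12 and gives the optional Week 52 sample becomes an Arm 3 completer. An Arm 3 patient sampled at relapse on day 200 becomes Arm 2.

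**Conclusion.** The point holds for RMS Arms 1–3 and for the LP row of the disposition table, on the reading that visits follow the Appendix 2 windows. Adherence to the randomised LP time cannot be read from that row, and per-arm completion is at or above its value by randomised arm.

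Under the assumed counts, Arm 2 is overstated by 12.5 to 14.3 points when 4 of 28 move out and none move in. The difference is zero if nobody moves. The real number of movers is unknown and may be small. Overall receipt of a second LP and the safety totals are not affected. This is a minor reporting point that is cheap to correct.

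**What to change.** In SAP 4.2, for Arms 1–3:

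- Report LP completion and disposition by randomised arm, with the denominator stated as ITT patients randomised to that LP time. Stating it matters because SAP Table 2 assigns disposition to the enrolled population while SAP 4.2 uses ITT.
- Add one cross-table of randomised arm by actual LP timing.
- State that the second LP used to set the actual arm is the scheduled one, not an optional relapse or optional Week 52 LP.
- Flag LPs outside the protocol's ±7 days. Grouping by randomised arm alone would not reveal lateness inside the wide CSF windows.

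Keep actual-arm grouping for the CSF biomarker summaries, where its stated reason applies. The cost is SAP wording and one extra table, since the IxRS provider already holds the assignment code (SAP 3.1). Reported LP completion may look slightly less favourable.

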4.3 ANALYSIS OF TREATMENT GROUP COMPARABILITY

For continuous variables, the mean, median, SD, minimum, and maximum will be calculated. For categorical variables, number and percentage in each category will be displayed. The units/categories to be used are indicated within the brackets and separated by commas.

Except where stated, all assessments of treatment group comparability will utilize the date of the baseline visit (not the date of the screening visit) as the reference point in time, unless otherwise stated. For Arm 4, the treatment baseline will be used when comparing to other arms.

Biomarker values for Arm 4 at pre-treatment baseline will be summarized separately and compared to Arm 1 baseline values.

4.3.1 Demographics and Baseline Characteristics

The following patient demographics and baseline characteristics will be summarized:

Age (years)

Age (years) group: (age categories < 40, \geq 40, and age categories < 18, \geq 18–<40, \geq 40–<55, $>$ 55)

Gender

Self reported race and ethnicity

Female and male reproductive statuses

Region (USA, Canada, EU)

Baseline Height, weight, and BMI

4.3.2 Multiple Sclerosis Disease History

Patient disease history summaries will include the following variables:

Duration since MS first symptoms (in years), categorical ($=<3$, $>3 - =<5$, $>5 - =<10$ and >10).

MS diagnosis categories (RRMS, SPMS, PPMS)

Duration since MS diagnosis (in years), categorical ($=<3$, $>3 - =<6$, $>6 - =<9$ and >9 ; $=<2$, $>2 - =<5$, $>5 - =<10$ and >10).

Previous disease-modifying therapy (DMT) treatment status (DMT-naïve vs. DMT-experienced)

Number of previous unique DMTs

Number of switches of previous DMTs

Last DMT before study enrollment

Duration of last DMT

Reasons for enrollment eligibility

Baseline EDSS (rounded) and categorical ($0 - <3$, $3 - <4$, $4 - <6$, $>=6$)

4.3.3 Baseline biomarker data

Patient baseline CSF and blood biomarker data summaries will include the variables described in Sections 2.2.1 and 2.2.2. The summaries may also be done by:

Previous disease-modifying therapy (DMT) treatment status (DMT-naïve vs. DMT-experienced).

4.3.4 Baseline MRI Data

Patient baseline MRI data summaries will be done as follows:

Number of Gd-enhancing T1 lesions at baseline and categorical (1, 2, 3, 4-8, 9-20, >20)

Number of T2 lesions at baseline and categorical (0-3, 4-5, 6-9, >9)

Volume of T2 lesions at baseline

Brain volume at baseline

4.4 EFFICACY ANALYSIS

All biomarker assessments (scheduled or unscheduled) will be summarized after applying visit windows. Summary of the visit windowing rules can be found in Appendix 2. See Module 3 for full visit window specifications. If multiple values of the same parameter occur within the same time window for blood biomarkers

Ocrelizumab—Genentech, Inc.

15/Statistical Analysis Plan ML29966

or regular lab values, the worst value for that parameter will be presented in the summary table. If multiple MRI scans occur within the same time window, the scan closest to the scheduled visit date will be included in the analysis.

All summaries will be done based on the ITT population and summaries will be provided by the actual arm, as determined by the actual timing of 2nd LP:

For patients randomized to Arm 1-3,

If the second LP date is missing then patient is included in the arm where originally randomized to;

Else:

Study Day of second LP (= date of the 2nd LP – 1st infusion start date +1)	Treatment Arm
≤126	Arm 1
127-266	Arm 2
≥267	Arm 3

Patients randomized to Arm 4 will be summarized as Arm 4 regardless of the timing of 2nd LP.

Unless otherwise specified and where appropriate, statistical tests, if any, will be performed at the two-sided 5% significance level. Corresponding 95% confidence intervals will be presented as appropriate. No corrections for multiple testing will be applied.

For biomarkers measured below the lower limit of quantification (LLOQ), numeric values will be imputed using half of the LLOQ.

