Patients in Arm 4 will receive two LPs, separated by a 12-week interval, before administration of the first dose of ocrelizumab. Patients in this arm will be asked if they are willing to give an optional CSF sample via LP 12 weeks after the ocrelizumab dose.

Patients in the PPMS cohort will receive an LP at the start of the study before dosing with ocrelizumab. Subsequently, they will receive a second LP at Week 52 following the first dose of ocrelizumab.

In the case of MS relapse or worsening (for PPMS patients) during the study, the patient should have an unscheduled visit and will be asked to receive an optional LP at the time of relapse or worsening (for PPMS patients). The patient will have another LP at the originally scheduled time based on their randomization, or if a relapse occurs after they have already given the second LP, the relapse LP will remain optional.

All patients will be evaluated for safety throughout the study.

In the case of early termination, the patient will be asked to have an early termination visit.

Number of Patients

Approximately 104 patients will be enrolled in this study; 88 patients with RMS and 16 patients with PPMS.

Target Population

Inclusion Criteria

General Inclusion Criteria

Patients must meet the following criteria for study entry:

- Signed Informed Consent Form
- Ability to comply with the protocol, in the investigator's judgment
- Age 18–55 years, inclusive

Ocrelizumab—Genentech, Inc.

43/Protocol ML29966, Version 4 (Global)

- For women of childbearing potential: agreement to remain abstinent (refrain from heterosexual intercourse) or use contraceptive methods that result in a failure rate of <1% per year during the treatment period and for at least 24 weeks after the last dose of study treatment or until their B cells have repleted, whichever is longer
 - A woman is considered to be of childbearing potential if she is postmenarcheal, has not reached a postmenopausal state (≥ 12 continuous months of amenorrhea with no identified cause other than menopause), and has not undergone surgical sterilization (removal of ovaries and/or uterus).
 - Examples of contraceptive methods with a failure rate of <1% per year include bilateral tubal ligation, male sterilization, established, proper use of hormonal contraceptives that inhibit ovulation, hormone-releasing intrauterine devices, and copper intrauterine devices.

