- ^b The Safety Follow-up Period will begin only if the patient discontinues from treatment early or completes the study and does not continue on ocrelizumab treatment (i.e., commercially available or from another source). Patients will be assessed in safety follow-up every 24 weeks for 48 weeks following the last infusion of ocrelizumab. After 48 weeks, if the peripheral blood B-cell count remains depleted, monitoring of the patient should continue at 24-week intervals until the B-cell count has returned to the baseline value or to the lower limit of the normal range, whichever is lower.
- ^c Biomarkers will be assessed via blood draws at Week 1 (pre-dose Day 1), Week 3 (pre-dose Day 15), and at timepoints noted from Weeks 12 through 52. Biomarkers will be assessed via LP in CSF before the first dose of ocrelizumab and from a second LP at Week 52 following the first dose of ocrelizumab.

Table 1 Study Cohorts and Overall Design

RMS Cohort		
	First LP	Second LP
Arm 1	Treatment baseline/Week 1	Week 12
Arm 2	Treatment baseline/Week 1	Week 24
Arm 3	Treatment baseline/Week 1	Week 52
Arm 4 (control arm)	Pre-treatment baseline/ Week -12	Treatment baseline/ Week 1
PPMS Cohort		
	First LP	Second LP
All PPMS patients	Treatment baseline/Week 1	Week 52

LP = lumbar puncture; PPMS = primary progressive multiple sclerosis; RMS = relapsing multiple sclerosis.

Note: Study Day 1 is the day of the first dose of study drug, and all relative day calculations are based on number of days from Study Day 1.

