Appendix 1 **Schedule of Activities for the RMS Cohort Arms 1–3 (cont.)**

- j If the screening assessment has been conducted within 14 days prior to baseline dosing, it does not need to be conducted again prior to baseline dosing.
- k Results should be available prior to dosing (*may* be taken up to 14 days prior to dosing) to ensure patient eligibility per the investigator's discretion (see Section 4.6.1).
- l Hematology will include hemoglobin, hematocrit, RBCs, WBC absolute and differential, ANC, and quantitative platelet count. Chemistry will include AST, ALT, GGT, total bilirubin, urea, uric acid, creatinine, potassium, sodium, calcium, and phosphorus. Standard urinalysis will be used to assess kidney function.
- m Serum β -hCG must be performed at screening in women of childbearing potential. Subsequently, urine β -hCG (sensitivity \geq 25 mIU/mL) must be collected. On infusion visits, the urine pregnancy test should be performed prior to methylprednisolone infusion in all women of childbearing potential. If positive, ocrelizumab should be withheld and pregnancy status confirmed with serum β -hCG test.
- n All patients must have negative HBsAg result and negative HepCAb screening tests prior to study enrollment. If HBcAb is positive at screening, HBV DNA measured by PCR must be negative. For those patients enrolled with negative HBsAg and positive total HBcAb, HBV DNA (PCR) must be repeated every 24 weeks during the treatment period.
- o CSF specimen will be obtained at Week 1 (baseline, pre-dose) and at either Week 12, 24 (pre-dose), or 52 according to randomization; AND at an unscheduled visit in case of relapse (two CSF samples per patient, unless consent for optional relapse sample is given). The collection of the CSF specimen should precede the brain MRI.
- p The brain MRI requires 2 business days to be quality checked before dosing of ocrelizumab. In order to facilitate scheduling before an ocrelizumab dose, the CSF specimen collection, followed by the brain MRI, may precede the administration of ocrelizumab by up to 7 business days.
- q To be obtained/Performed optionally in case of relapse or suspected relapse.
- r Local blood flow cytometry and blood TBNK/B-cell subset panel samples (where indicated at the same timepoints as CSF, including optional relapse CSF) should be collected on the same day and as close as possible in time to the CSF sample, prior to ocrelizumab administration by up to 7 days.

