4.4.2 Exploratory Endpoints

4.4.2.1 Summaries of Exploratory Endpoints Over Time

For RMS patients in Arm 4, values at pre-treatment baseline and treatment baseline, and change and percent change from treatment baseline to post-baseline visits will be summarized.

For RMS patients in arms 1-3 and PPMS patient arm, CSF biomarker endpoints, blood biomarker endpoints and MRI biomarker endpoints stated in Section 2.2.2 will be summarized over time following the same rule as the primary efficacy endpoint, as stated in Section 4.4.1. The median (IQR) value of CSF and blood biomarkers at pre-treatment baseline, treatment baseline and post-baseline visits will be plotted over time and color coded by each arm. Scatter points of data will be laid over the median (IQR) plot for blood NfL level, CD19+ B cell and CD3+ T cell numbers.

Mean (SD) of MRI biomarker endpoints will be summarized over time.

For blood biomarkers, patient arms will also be pooled to look at the effect of ocrelizumab over time.

4.4.2.2 Comparison between Arm 1 and Arm 4

For patients in Arm 4, changes from pre-treatment baseline to treatment baseline will be compared to Arm 1 change from treatment baseline to Week 12 through an ANCOVA model adjusting for baseline DMT status (DMT naïve vs. DMT experienced) and baseline biomarker level for the following endpoints:

- CSF CD19+ B cell, CD3+ T cell and NfL
- Blood CD19+ B cell, CD3+ T cell and NfL

If data are highly skewed, ANCOVA model will be based on percent changes.

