4.4.4 Subgroup Analyses

The primary efficacy endpoints (change in levels of NfL in CSF, change in number of CD19 + B cells and change in number of CD3 + T cells in CSF) will be further summarized for DMT-naïve and DMT-experienced patients separately, and for patients who experienced at least one relapse during the study and patients experienced no relapse separately.

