Week 192	1344	>=1,261 and <=1,428	Window is from Week 180+1 day to Week 204
Week 216	1512	>=1,429 and <=1,596	Window is from Week 204+1 day to Week 228
Week 240	1680	>=1,597	Window is Week 228+1 day to end of LTE

Visit window for MRI biomarkers (Arm 1-4 & PPMS):

Report Visit Label	Nominal study days (from baseline)	Visit window (in terms of study days from baseline)	Notes
Week -12 (Arm 4)	-84	<=-28	
Baseline (Arm 4)	1	>-28 and <=1	Give a 4-week window for baseline visit

Baseline (Arm 1-3 & PPMS)	1	<=1	
Week 12	84	2<= and <=126	Window is from Day 2 until Week 18
Week 24	168	127<= and <=266	Window is from Week 18+1 day until Week 38
Week 52	364	267 - < LTE Day 1 (if entered LTE) 267 – patient end of main study date (if not entered LTE)	Window is from Week 38 +1 day
Week 96	672	LTE Day 1 - <=840	Window is from LTE Day 1 to Week 120
Week 144	1008	>=841 and <=1,176	Window is from Week 120+1 day to Week 168
Week 192	1344	>=1,177 and <=1,512	Window is from Week 168+1 day to Week 216
Week 240	1680	>=1,513	Window is from Week 216+1 day to end of LTE

*Early withdrawal, B cell monitoring and safety follow up 1 and 2 excluded from windowing

Visit window for CSF Biomarkers (Arm 1-4 & PPMS):

Report Visit Label	Nominal study days (from baseline)	Visit window (in terms of study days from baseline)	Notes
Week -12 (Arm 4)	-84	< -14	
Baseline (Arm 4)	1	-14 - 1	Give a 2-week window for baseline visit
Baseline (All patients except Arm 4)	1	<=1	
Week 12 (All patients)	84	2 - 126	
Week 24 (All patients)	168	127-266	
Week 52 (All patients)	364	267 - < LTE Day 1 (if entered LTE) 267 – patient end of main study date (if not entered LTE)	
Week 144 (All patients)	1,008	LTE Day 1 - <=1,344	Window is from LTE Day 1 to Week 192

Week 240 (All patients)	1,680	$\geq 1,345$	Window is from Week 192+1 day to end of LTE
-------------------------	-------	--------------	---

Visit window for EDSS:

Report Visit Label	Nominal study days (from baseline)	Visit window (in terms of study days from baseline)	Notes
Screening (Arm 4)	N/A	≤ -97	
Screening (Arm 1-3 & PPMS)	N/A	≤ -13	
Week -12 Pre-Baseline (Arm 4)	-84	$-97 - \leq -14$	Give a 2-week window for baseline visit
Baseline (Arm 1-3 & PPMS)	1	$-13 - \leq 1$	Give a 2-week window for baseline visit
Baseline (Arm 4)	1	$-14 - \leq 1$	Give a 2-week window for baseline visit
Week 12 (All Patients)	84	$2 \leq \text{and} \leq 126$	Window is from Day 2 until Week 18
Week 24 (All Patients)	168	$127 \leq \text{and} \leq 210$	

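### Visit windows in SAP 4.4 and Appendix 2 show relapse-triggered CSF samples as scheduled visits; the blood duplicate rule and the EDSS Week 52 window also need correcting

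*SAP*

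**What the plan says.** **CSF (primary endpoints).** SAP 4.4 states that "All biomarker assessments (scheduled or unscheduled) will be summarized after applying visit windows". In SAP Appendix 2 the CSF row that opens "Week 12 (All patients" covers Days 2-126. Week 24 covers Days 127-266, and Week 52 runs from Day 267 to the extension or the end of the main study. SAP 4.4.1 tabulates CSF NfL, CD19+ and CD3+ by arm at these visits and excludes nothing. Protocol 3.1 supplies the unscheduled samples: at relapse, "the patient should have an unscheduled visit and will be asked to receive an optional LP at the time of relapse". Footnote q of Protocol Appendix 1 widens this: "To be obtained/Performed optionally in case of relapse or suspected relapse".

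**Arms.** Under SAP 4.4, "summaries will be provided by the actual arm, as determined by the actual timing of 2nd LP", with cuts after Days 126 and 266. Protocol Table 1 ("Study Cohorts and Overall Design") gives each arm one second LP. SAP 4.4.2.2 compares the Arm 4 pre-treatment change with the "Arm 1 change from treatment baseline to Week 12 through an ANCOVA model".

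**Duplicates.** SAP 4.4 takes the worst value for blood biomarkers and routine labs and the closest scan for MRI. It prints no rule for CSF or EDSS and refers to Module 3 for full window specifications. The Appendix 2 blood table takes the record closest to Day 1 as baseline for Arms 1-3 and PPMS.

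**EDSS.** Appendix 2 gives Week 36 as Days 211-294, Week 48 as Days 295-350, and Week 52 as starting at Day 267.

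**The concern.** A relapse LP is taken because disease is active, not because a visit is due. Protocol 1.1 says that CSF NfL has been correlated with clinical relapses, so such a value may raise post-treatment NfL wherever it lands. A cell made up only of these samples would still be plotted as a point on that arm's time course.

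For blood, *worst* has no stated direction for NfL, CD19+ or CD3+. For Arms 1-3, a post-baseline value chosen as worst is set against a baseline chosen as closest. This reaches the blood endpoints in the Arm 1 versus Arm 4 ANCOVA. If safety follow-up draws count as Week 52, B-cell counts taken long after the last infusion could be reported as on-treatment values.

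For EDSS, one score can belong to two visits.

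**Working it through.** **Plan's own figure.** SAP 2.3 assumes NfL 860 (SD 780) falling to 602 (SD 310) pg/mL with r = 0.6. SD of change = √(780² + 310² − 2 × 0.6 × 780 × 310) = √414,340 = 643.7, against 643 in the plan. A two-sided 5% paired t-test for a change of 258 needs N = 51 (power 80.2%), which reproduces the plan. Nothing below alters that number.

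**CSF cells.** Arms 1-3 × Weeks 12, 24 and 52 = 9 cells.
- The scheduled second LP fills 3: Arm 1/Week 12, Arm 2/Week 24, Arm 3/Week 52.
- The optional Week 52 LP for Arms 1 and 2 (Version 5 synopsis in SAP Appendix 1) fills 2.
- Left with no planned source except relapse LPs: Arm 1/Week 24, Arm 2/Week 12, Arm 3/Week 12 and Arm 3/Week 24, so 4 cells.

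**Expected relapse LPs.** Assumptions: 0.086-0.186 relapses per patient-year (Phase II 300 mg × 2 group, Protocol 1.2.1.2) apply here at a constant rate; arm sizes are 16, 28 and 28 with no dropout; there is one LP per relapse. LP uptake is not given, so it ranges from 0 to 100%.
- Window lengths: 126 − 2 + 1 = 125 days; 266 − 127 + 1 = 140 days.
- Four cells: (16 × 140 + 28 × 125 + 28 × 125 + 28 × 140)/365 = 13,160/365 = 36.05 patient-years, giving 3.1-6.7 LPs at full uptake.
- Arm 1, Week 12 window: 16 × 125/365 = 5.48 patient-years, giving 0.5-1.0.
- Arms 1-3, Days 2-364: 72 × 363/365 = 71.6 patient-years, giving 6.2-13.3.
- At zero uptake every count is 0.

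**What one value could do in Arm 1.** This applies only if a relapse value is actually used. The NfL excess is not in the documents; 310-780 pg/mL (the two SDs in SAP 2.3) is an assumption. Shift in a mean of 15 = 310/15 = 21 to 780/15 = 52 pg/mL, or 8-20% of 258. The 258 was planned for Arms 2 and 3 and serves only as a yardstick.

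**Blood.** If two values in a window are exchangeable and normal, taking the more extreme biases the result by about 0.56 within-patient SD; with three values, about 0.85 SD (simulation). For an RMS patient last infused on Day 336, safety follow-up falls on Days 336 + 168 = 504 and 336 + 336 = 672. Both lie after Day 351, where the blood Week 52 window opens. Protocol Appendix 1 schedules the blood TBNK/B-cell panel at Week 52 and at safety follow-up, so up to 3 draws could share that label. Protocol 5.1.1.1.4 reports repletion from 27 weeks after the last infusion, so a 48-week count may already have recovered.

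**EDSS overlap.** With Week 36: 294 − 267 + 1 = 28 days. With Week 48: 350 − 295 + 1 = 56 days. Total 84. All 15 on-time Week 48 days (336 ± 7 = 329-343) also count as Week 52. Starting Week 52 at Day 351 removes the overlap and keeps all 15 on-time Week 52 days (357-371).

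**The case against.** A reader might infer that relapse LPs contaminate the Arm 1 versus Arm 4 ANCOVA outright. The documents do not support that. A patient is normally in Arm 1 because a scheduled LP fell on or before Day 126, so a relapse LP in that window is a duplicate. It counts only if the scheduled LP is missing or the tie-break picks it, and Module 3, which is not available, may settle the tie-break. Protocol 6.4.2 also permits optional samples in that exploratory comparison, so using them is not a departure from the protocol. Only the Arm 1 side is exposed: Protocol Appendix 2 (footnote b) offers Arm 4 relapse LPs after both control LPs.

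A reader might also infer that a relapse LP can move a patient to another arm. Protocol 3.1 distinguishes the second LP from the relapse LP, and Table 1 lists the second LP by scheduled week. The SAP should say so, but reassignment is not the natural reading.

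Nor is it established that safety follow-up draws enter blood Week 52. SAP 2 extends the main period to data cutoff or end of study for patients without a Week 72 dose, while SAP 4.9 assigns safety follow-up data to the LTE Final Analysis. The MRI and EDSS tables carry a footnote excluding safety follow-up and the blood table does not, but that note may have been meant generally. The closest-to-Day-1 baseline could likewise be an intended exception.

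The primary tables are descriptive, the plots use medians with individual points, and log transformation, percent-change ANCOVA and a Mann-Whitney analysis are available. SAP 4.4.4 further summarizes the primary endpoints "for patients who experienced at least one relapse during the study and patients experienced no relapse separately". These limit the effect but are only a partial check: the no-relapse summary drops relapsing patients' scheduled LPs, keeps LPs for suspected relapses that were not confirmed, and does not cover the ANCOVA.

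What stands is the printed text: unscheduled CSF samples are included, *worst* has no direction, and the EDSS windows overlap.

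**Conclusion.** The concern holds for three printed rules and should be fixed.

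1. **CSF:** the clear effect is on 4 of 9 primary cells, holding about 3-7 LPs at full uptake and 0 at zero uptake, under the assumed relapse rates. The resulting NfL bias cannot be derived from the documents and is zero if no relapse LP is taken. In the other cells, and in the Arm 1 versus Arm 4 ANCOVA, the effect is conditional on a missing scheduled LP or on the tie-break.
2. **Blood (exploratory):** the worst-value rule is undefined in direction and differs from the baseline rule. The upper end of Week 52 is unclear until SAP 2 and SAP 4.9 are reconciled.
3. **EDSS (exploratory):** the 84-day overlap is certain but minor. EDSS change is only a possible endpoint in Protocol 6.4.2 and is not listed in SAP 2.2.2.

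**What to change.** Amend SAP 4.4 and Appendix 2:

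- (a) Report LPs triggered by relapse or suspected relapse separately from the by-visit primary CSF tables. Keep scheduled and non-relapse optional LPs. Use the scheduled LP in the Arm 1 versus Arm 4 ANCOVA, with relapse samples added only as a sensitivity analysis. Present this as a choice to reduce bias, since Protocol 6.4.2 allows optional samples there.
- (b) State that the second LP in the actual-arm rule is the scheduled second LP.
- (c) For blood biomarkers, use the value closest to the scheduled visit day and keep *worst* for safety labs. Exclude safety follow-up and B-cell monitoring from Week 52, and reconcile SAP 2 with SAP 4.9. Settle the Week 3 reference day, which is Day 15 in the protocol schedule and Day 21 in the SAP blood table.
- (d) Start EDSS Week 52 at Day 351, as the blood table does.
- (e) Apply the closest-to-scheduled-day rule to remaining CSF and EDSS duplicates.

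**Cost.** SAP wording and programming. A few relapse samples leave the main tables, and a patient with only a relapse LP has no post-treatment value there; Arms 2 and 3 enrol 56 for 51 needed, which allows for 5 missing. The study is open-label, Interim Analysis 1 is done, and the samples set aside may be high ones, so the change should be documented as made after that analysis and the relapse samples still shown.
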